#### 3.2. Secondary Endpoints

The secondary endpoints for the study are:

- Comparison of primary and secondary efficacy parameters between doses
- Incidence of adverse events (AEs), serious adverse events (SAEs), and changes in laboratory test results
- Bone marrow improvement:
  - Bone marrow response rate at weeks 12, 24, and 36
  - Duration of bone marrow response
- Hemoglobin improvement

Baseline Status	Categories of Hemoglobin Improvement
Subjects who are transfusion dependent ( $\geq 2$ units PRBC every 4 weeks for 12 weeks prior to or after C1D1), regardless of baseline hemoglobin level	Percent of subjects with Red cell transfusion independence (no transfusions for $\geq 12$ consecutive weeks)  OR  50% reduction in RBC transfusions for $\geq 12$ consecutive weeks
Subjects with baseline hemoglobin $< 100$ g/L AND Not transfusion dependent	Percent of subjects with $\geq 10$ g/L and $\geq 20$ g/L increase in hemoglobin for $\geq 12$ consecutive weeks without transfusions

- Platelet improvement

Baseline Status	Categories of Platelet Improvement
Subjects who are transfusion dependent ( $\geq 2$ platelet transfusions in any 12 weeks prior to or after C1D1), regardless of baseline platelet level	Percent of subjects with: Platelet transfusion independence (no transfusions for $\geq 12$ consecutive weeks)  OR

Platelet transfusion = either 1 unit apheresed (single donor) platelets or 4-8 units pooled random donor platelets	50% reduction in platelets transfusions for $\geq$ 12 consecutive weeks
Subjects with $25 < \text{baseline platelets} < 50 \times 10^9/\text{L}$  AND Not platelet transfusion dependent	Percent of subjects with: Doubling of baseline platelet count for $\geq$ 12 consecutive weeks without platelet transfusions  OR  Platelet count $> 50 \times 10^9/\text{L}$ for $\geq$ 12 consecutive weeks without platelet transfusions,
Subjects with baseline platelet count $< 25 \times 10^9/\text{L}$  AND Not platelet transfusion dependent	Percent of subjects with: Doubling of baseline platelet count for $\geq$ 12 consecutive weeks without platelet transfusions  OR  Platelet count $> 25 \times 10^9/\text{L}$ for $\geq$ 12 consecutive weeks without platelet transfusions

- Hematologic improvement

Baseline Status	Categories of Hematologic Improvement

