## 5. STAGE 2 SELECTION OF STUDY POPULATION

### 5.1 Study Population

#### 5.1.1. Inclusion Criteria

This Phase 2 study will enroll up to 111 subjects with MF, 27 in Stage 1, and up to an additional 84 subjects in Stage 2

Each subject must meet all of the following inclusion criteria to be enrolled in the study:

1. Subjects must be  $\geq 18$  years of age at the time of signing the Informed Consent Form (ICF);
2. Subjects must voluntarily sign an ICF;
3. Subjects must have a pathologically confirmed diagnosis of PMF as per the WHO diagnostic criteria (see [APPENDIX C](#)) or post ET/PV MF;
4. At least Grade 2 marrow fibrosis according to the WHO Grading of Bone Marrow Fibrosis ([APPENDIX D](#));
5. Intermediate -1, intermediate -2, or high risk disease according to the IWG-MRT Dynamic International Prognostic Scoring System (see [APPENDIX E](#));
6. A bone marrow biopsy must be performed within four weeks prior to Cycle 1 Day 1 treatment to establish the baseline fibrosis score;
7. Subjects must not be candidates for ruxolitinib based on EITHER:
  - a. Platelet count  $< 50 \times 10^9/L$ , OR
  - b. Hgb  $< 100$  g/L have received  $\geq 2$  units PRBC in the 12 weeks prior to study entry, and be intolerant of or had inadequate response to ruxolitinib;
8. Subjects must have an Eastern Cooperative Oncology Group (ECOG) Performance Status of 0-2. ([APPENDIX F](#));
9. Life expectancy of at least twelve months;
10. At least four weeks must have elapsed between the last dose of any MF-directed drug treatments for myelofibrosis (including investigational therapies) and study enrollment;
11. Recovery to  $\leq$  Grade 1 or baseline of any toxicities due to prior systemic treatments, excluding alopecia;

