### **7.2. Study Entrance Criteria**

At Screening, each subject will be reviewed for eligibility against the study entrance criteria. Subjects who do not meet the study entrance criteria will not be allowed to participate in the study. The reason(s) for the subject's ineligibility for the study will be documented. All subjects must undergo a bone marrow biopsy for grading of bone marrow fibrosis. Subjects with a myelofibrosis Grade < 2, according to the WHO criteria ([APPENDIX D](#)), as determined by the local pathologist, will not be allowed to participate in the study.

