2.2.2 Secondary Efficacy Endpoints

The secondary efficacy endpoints are as follows for:

Stage 1:

- Bone Marrow MF grade shifts relative to baseline over time
- Modified Myeloproliferative Neoplasm-Symptom Assessment Form Total Symptom Score (MPN-SAF TSS) changes from baseline over time

Stage 2:

- Bone Marrow improvement:
 - Bone marrow (BM) response rate (MF Grade) at each visit (reduction of 1 grade versus baseline)
 - Duration of BM response defined for responding subjects as time from first decrease from baseline of one grade to time of return to baseline levels. If no return to baseline levels or worse than baseline then duration will be censored at the last BM assessment.
- Hemoglobin improvement (number and percentage of subjects):
 - For red blood cell transfusion dependent subjects at baseline (at least 2 units every 4 weeks for 12 weeks prior to Cycle [C]1Day [D]1), improvement is defined as either:
 - 1) absence of any packed red blood cells (PRBC) transfusion during any consecutive 12 weeks interval with hemoglobin level of ≥80g/L

OR

- 2) at least a 50% reduction in PRBC transfusions for 12 consecutive weeks with hemoglobin level of ≥80g/L
- For red blood cell transfusion independent subjects improvement is defined as:
 - ≥10 g/L increase in hemoglobin level for 12 consecutive weeks without transfusions
- Platelet improvement (number and percentage of subjects)

- For transfusion dependent subjects at baseline, improvement is defined as either:
- 1) becoming transfusion independent for 12 consecutive weeks

OR

- 2) reduction in transfusions need ≥50% from baseline for 12 consecutive weeks
- For transfusion independent subjects with baseline platelet count below 100^9/L, improvement is defined as:
 - ≥50% increase in the number of platelet for 12 consecutive weeks or normalization of platelet count (above lower limit normal)
- Symptom improvement:

Percent of subjects with 50% reduction in MPN-SAF TSS from baseline over time(Tefferi 2013)

• Percent of subjects with complete response, partial response, clinical improvement, stable disease and progressive disease according to IWG-MRT criteria.

2.2.3 Exploratory Efficacy Endpoints

The exploratory efficacy endpoints are as follows for:

Stage 1:

- Bone marrow biopsy results for:
 - Myeloblasts (%), at each time point and change from baseline
 - Cellularity (%), at each time point and change from baseline
 - Collagen and reticulin grade shifts relative to baseline over time

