- Myeloblasts and cellularity will be presented at baseline, Weeks 12 and 24 as well as change from baseline
- Collagen grade shifts relative to baseline at Weeks 12 and 24.

The modified MPN-SAF TSS will be presented descriptively at baseline and at the beginning of each cycle (Cycle 2 onward). In addition, the number of subjects with \geq 25% and \geq 50% reduction relative to baseline at the beginning of each cycle (Cycle 2 onward) will be presented.

Stage 2:

Duration of effect of the three doses on reduction in bone marrow fibrosis:

- To assess the duration of effect of the three doses on bone marrow improvement a
 Kaplan-Meier plot will be provided. Duration of BM improvement will be defined for
 responding subjects as time from first decrease from baseline of one grade to time of
 return to baseline levels. If no return to baseline levels then duration will be
 censored at the last BM assessment
- Effect and duration of effect of the three doses on disease related anemia, thrombocytopenia, and constitutional symptoms: For patients with improvement, the duration of improvement is defined as the number of weeks of improvement from the first12 weeks of improvement period.

IWG-MRT response will be summarized by treatment group at each visit by percent of subjects with complete response, partial response, clinical improvement, stable disease and progressive disease according to IWG-MRT criteria.

4.4.3 Exploratory Efficacy Endpoints

The exploratory endpoints will be summarized using tables, listings and graphs as appropriate.

4.4.4 Sensitivity Analyses

For Stage 2, a non-stratified analysis of BMRR will be computing as a sensitivity analysis.

4.4.5 **Subgroup Analyses**

Stage 1:

• Primary endpoint results will be presented by risks groups (intermediate-1, intermediate-2, or high risk subjects).

Stage 2:

- Primary endpoint results will be presented:
 - by risks groups (intermediate-1, intermediate-2, or high risk subjects)
 - for each strata separately (baseline anemia alone, baseline thrombocytopenia alone, baseline anemia and thrombocytopenia)
 - by transfusion status at baseline with transfusion dependency defined as: ≥ 2
 units PRBC every 4 weeks for 12 weeks prior to or after C1D1
 - by PTX-2 level at baseline classify by High/Low category (median as the cutoff)

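### SAP 2.2.2 and 4.4.2 define the end of a marrow response differently; read literally, 4.4.2 censors a responder who worsens past the baseline grade as still responding.

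*SAP*

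**What the plan says.** The protocol makes duration of the marrow effect a secondary objective (2.2) and lists "Duration of bone marrow response" among the secondary endpoints (3.2), but gives no event or censoring rule. The rule appears only in the SAP, in two places.

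- **SAP 2.2.2 (Stage 2):** "Duration of BM response defined for responding subjects as time from first decrease from baseline of one grade to time of return to baseline levels". It then says: "If no return to baseline levels or worse than baseline then duration will be censored at the last BM assessment".
- **SAP 4.4.2 (Stage 2), which specifies the Kaplan-Meier plot:** duration is defined for "responding subjects as time from first decrease from baseline of one grade to time of" return to baseline. It then says "If no return to baseline levels then duration will be" censored at the last marrow assessment. Worsening past baseline is not mentioned.

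SAP 2.2.2 also describes by-visit response in brackets as "reduction of 1 grade versus baseline". The primary endpoint (Protocol 3.1; SAP 2.2.1 and 4.4.1) requires a reduction of at least one grade.

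**The concern.** A return to baseline and a grade worse than baseline are both losses of the response, and the second is the clearer loss. Section 4.4.2 names only the first as an event. A program that tests for a later grade equal to baseline would carry a worsened responder to the last biopsy as a censored, ongoing response. That lengthens the recorded time or removes an event, and the error cannot go the other way. Because 4.4.2 specifies the plot, it is the section most likely to be programmed. Section 2.2.2 does not clearly override it.

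**Working it through.** The documents state no figure for duration, so there is nothing to reproduce. The check compares the two wordings, finds which subjects they can affect, and sizes one case.

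**1. The two censoring sentences.** In 4.4.2, no return to baseline leads to censoring. Section 2.2.2 allows two readings:
- (a) Censor when there is neither a return to baseline nor a worse grade.
- (b) Censor when there is no return, and also when the grade is worse.

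Under (b), if a return means a grade exactly equal to baseline, a subject who jumps past baseline already has no return, so the extra words add nothing. They do work only under (a), so (a) is the sensible reading. Even then, the only event date defined is the return to baseline. The worsened subject is not censored but has no stated event time.

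**2. Who can be affected.** Inputs:
- Entry requires "At least Grade 2 marrow fibrosis according to the WHO Grading of Bone Marrow Fibrosis" (Protocol 5.1.1).
- MF-3 is the top grade (Protocol Appendix D), so an MF-3 baseline cannot be exceeded.
- Eligibility is graded locally: a lower grade, "as determined by the local pathologist, will not be allowed to participate in the study" (Protocol 7.2). Response uses the central grade, so a central baseline of MF-1 is possible.
- Main-stage biopsies are at Weeks 12, 24 and 36 (Protocol 7.11.1 and 7.16).

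Three biopsies with grades 0 to 3 give 4³ = 64 paths. For baseline grade b, paths that never fall below b number (4 − b)³, and the rest are responder paths. Each responder path was scored twice: event if a later grade equals b (literal 4.4.2), and event if a later grade is b or higher.

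| Central baseline | Responder paths | Paths where the rules differ |
|---|---|---|
| MF-3 | 64 − 1 = 63 | 0 |
| MF-2 | 64 − 8 = 56 | 16 |
| MF-1 | 64 − 27 = 37 | 16 |

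These are counts of possible paths, not probabilities. All 16 MF-2 paths contain a rise from MF-0 or MF-1 to MF-3 between consecutive biopsies. In 8 the time is unchanged but an event becomes a censored time. In 6 a 12-week event becomes 24 weeks censored. In 2 a 12-week event becomes a 24-week event. Every difference goes toward longer duration.

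**3. One subject.** Baseline MF-2; MF-1 at Week 12; MF-3 at Weeks 24 and 36.
- Literal 4.4.2: 36 − 12 = 24 weeks, censored.
- Event at equal or worse: 24 − 12 = 12 weeks, event.

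**4. Effect on the curve (assumed numbers).** Protocol 10.1 assumes 46% response with 24 subjects per arm: 0.46 × 24 = 11.04, about 11 responders. Suppose all respond at Week 12, 3 are back at baseline at Week 24, and 1 other has jumped past baseline at Week 24.
- Literal 4.4.2: S(12 weeks) = 1 − 3/11 = 0.727.
- Event at equal or worse: S(12 weeks) = 1 − 4/11 = 0.636.
- Difference: 1/11 = 9.1 points.

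With 84/3 = 28 enrolled per arm, 0.46 × 28 = 12.88 responders and one case is worth 1/12.88 = 7.8 points. With no such case the two curves coincide.

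**The case against.** The strongest reply is that 2.2.2, where the endpoint is defined, does address worsening and on its natural reading does not censor it. Section 4.4.2 would then be a shortened repeat, not a contrary rule. A return to baseline levels could also be understood as losing the improvement, whatever the exact grade. In addition, the affected path needs a baseline below MF-3 and a jump over the baseline grade in about 12 weeks, and the documents give no rate for that.

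Most of this stands, and it rules out three stronger inferences.

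- A reader might infer that the SAP as a whole censors worsened responders, so that duration is overstated. The documents do not establish that: the sensible reading of 2.2.2 points the other way, and bias arises only if 4.4.2 is followed literally and such a subject exists.
- A reader might infer that only MF-2 baselines are exposed. Local eligibility grading leaves a central MF-1 baseline possible.
- A reader might take the bracketed one-grade wording to exclude two-grade reductions from by-visit response. Protocol 3.1 and SAP 2.2.1 and 4.4.1 settle response as at least one grade, so the bracket is shorthand.

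What the reply does not remove is that the section specifying the plot omits worsening, and that neither section dates it as an event. Nor is the path confined to 12-week gaps. SAP 4.8 repeats secondary endpoints on the extension population where applicable, and there biopsies are optional every 12 weeks with a window of 6 weeks either side (Protocol Appendix J).

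**Conclusion.** The two SAP sections are inconsistent on when a marrow response ends, and 4.4.2 taken literally gives the wrong result in a case that can occur. Any resulting bias in the Kaplan-Meier duration is upward. It is confined to responders with a central baseline below MF-3 who pass from below to above that grade without a biopsy at it. Their number is not given. The figure of about 9 points per case assumes 11 responders, all at risk, and that one such subject exists; it is an illustration, not an estimate. The primary response rate and its comparison with the 10% threshold do not use this rule. Severity is minor.

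**What to change.** In SAP 2.2.2 and 4.4.2, use the same sentence: *Loss of response is the first BM assessment after response with a central MF grade equal to or worse than baseline; subjects with no such assessment are censored at their last BM assessment.* For consistency with the primary endpoint, write *at least 1 grade* in the by-visit response and in the start of duration. Check that the program tests for a grade equal to or above baseline. The cost is a few words in two sections and, if needed, one condition in the code. No new data are required.

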Subjects with both Hemoglobin $< 100 \text{ g/L}$ and Platelets $< 50 \times 10^9/\text{L}$	Percent of subjects who have EITHER Hemoglobin improvement OR Platelet improvement as described above and no worsening of hemoglobin or platelets from baseline
Subjects with only Hemoglobin $< 100 \text{ g/L}$	Percent of subjects who have Hemoglobin improvement as described above  AND Did not develop platelets $< 50 \times 10^9/\text{L}$
Subjects with only Platelets $< 50 \times 10^9/\text{L}$	Percent of subjects who have Platelet improvement as described above  AND Did not develop Hemoglobin $< 100 \text{ g/L}$ or new transfusion dependence

- Symptom improvement:

- Percent of subjects with 25% and 50% reduction in MPN-SAF Total Symptom Score from baseline at Week 36
- Mean change from baseline in EORTC QLQ-C30 at 36 weeks
- Duration of all improvement parameters listed above
- Percent of subjects with complete response, partial response, clinical improvement, stable disease, and progressive disease according to IWG-MRT criteria (Tefferi 2013, APPENDIX B)

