#### **10.6.1.3.3. Analyses of quantitative secondary and exploratory efficacy endpoints:**

Descriptive statistics for quantitative variables (see Section 10.3.2) will be computed, together with the 95% CI of the mean (or median depending on the variable)

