3.3 DATA MONITORING COMMITTEE

Stage 1 had no Data Monitoring Committee (DMC) in place.

In Stage 2, a DMC was established for purposes of independent assessment of safety during study conduct.

4. STATISTICAL METHODS

Except where specified, all continuous variables will be summarized by treatment group with descriptive statistics (the number of non-missing values, mean, standard deviation, median, minimum, and maximum). All categorical variables will be summarized with frequency counts and percentages, by treatment group.

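### Stage 2 duration of anemia, thrombocytopenia and symptom improvement is a week count with no end event or censoring, so long durations are biased short.

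*SAP*

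**What the plan says.** Protocol 3.2 makes duration a secondary endpoint for every improvement measure: "Duration of all improvement parameters listed above". Protocol 2.2 names duration of effect of the three doses on anemia, thrombocytopenia and constitutional symptoms as a secondary objective.

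SAP 4.4.2 (Stage 2) handles duration in two adjacent bullets.

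- **Marrow response.** The clock runs from the first one-grade decrease to return to baseline. Without a return, duration is "censored at the last BM assessment", and a "Kaplan-Meier plot will be provided". SAP 2.2.2 repeats the rule: "If no return to baseline levels or worse than baseline then duration will be censored at the last BM assessment".
- **The three other measures (anemia, thrombocytopenia, symptoms).** Among subjects who improve, the SAP states only that "the duration of improvement is defined as the number of weeks of improvement", with the count tied to the initial 12-week period. Nothing more is said.

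No other section fills the gap. SAP 4.9 rules out imputation and does not address improvements that are still present. SAP 4.8 extends the secondary endpoints to the open-label extension (OLE) where applicable, without a censoring rule. The fallback is the general rule opening SAP section 4, that "all continuous variables will be summarized by treatment group with descriptive statistics". Protocol 10.6.1.3.3 is similar: "Descriptive statistics for quantitative variables (see Section 10.3.2) will be computed, together with the 95% CI of the mean"; for some variables the median takes its place.

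**The concern.** A week count can only record what was observed. If a subject is still improved at the last assessment, the true duration is longer than the count by an unknown amount. A mean or median that treats the count as complete therefore partly measures follow-up after onset.

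Main-stage follow-up is short for this purpose. The SAP's Stage 2 label means the main stage (SAP section 2), which gives way to the OLE at Cycle 10, i.e. week 36 (SAP 4.8). The hemoglobin and platelet definitions in SAP 2.2.2 mostly require 12 consecutive weeks, so an improver who starts late has little time left in which loss could be seen. The protocol also allows for 15% discontinuation, and a subject who leaves while improved is truncated in the same way.

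At stake is a named secondary objective: whether the doses differ in how long the benefit lasts. Protocol 10.6.1.3.4 plans pairwise comparisons between arms for all categorical or quantitative secondary endpoints, so any distortion from onset timing or early withdrawal would carry into those tests.

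**Working it through.** The documents give no figure for these durations, so there is nothing to reproduce. The check below shows the direction of the bias and a range for its size.

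**Inputs from the documents.** Nine 4-week cycles give 9 × 4 = 36 weeks (protocol 4.1.3). An end-of-study visit about 28 days later collects blood counts, transfusions and MPN-SAF (protocol 8.6), so observation can reach about week 40. The improvement period is 12 weeks (SAP 4.4.2).

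**Assumptions not in the documents.** Onset is uniform over weeks 0 to 20. True duration T is 12 weeks plus an exponential tail, with overall median m = 16, 24, 36 or 64 weeks. There is no dropout.

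**Formulas.** The tail rate is r = ln 2 / (m − 12). With a week-36 cut, follow-up from onset, F, is uniform on 16 to 36 weeks. The plain count is min(T, F).

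- For t from 16 to 36: P(count > t) = exp(−r(t − 12)) × (36 − t)/20. The plain median is where this equals 0.5.
- Share ongoing: P(T > F) = [exp(−4r) − exp(−24r)] / (20r).
- Plain mean: 12 + (1 − share ongoing)/r. True mean: 12 + 1/r.

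**Example, m = 24.** r = 0.6931/12 = 0.05776. At t = 20.1, exp(−0.05776 × 8.1) × 15.9/20 = 0.626 × 0.795 = 0.498, so the plain median is about 20.1. Share ongoing = (0.7937 − 0.2500)/1.155 = 0.47. Plain mean = 12 + 0.529/0.05776 = 21.2, against a true mean of 12 + 17.3 = 29.3.

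| True median | Plain median | Kaplan-Meier median | Ongoing | True mean | Plain mean |
|---|---|---|---|---|---|
| 16 | 16.0 | 16.0 | 14% | 17.8 | 17.0 |
| 24 | 20.1 | 24.0 | 47% | 29.3 | 21.2 |
| 36 | 22.5 | not reached (edge of follow-up) | 68% | 46.6 | 23.2 |
| 64 | 24.2 | not reached | 83% | 87.0 | 24.6 |

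True medians of 24, 36 and 64 weeks are squeezed into plain medians of about 20 to 24. At m = 36 the true survival function equals exactly 0.5 at week 36, so whether Kaplan-Meier reaches its median there is a matter of chance.

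**Week-40 cut, m = 36.** F is uniform on 20 to 40 and r = 0.02888. At t = 25.3, exp(−0.02888 × 13.3) × 14.7/20 = 0.681 × 0.735 = 0.501, so the plain median is about 25.3. The bias is smaller but remains.

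**Onset timing alone.** Give two groups the same true duration (m = 36) and a week-36 cut.

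- Onset in weeks 0 to 8 (F uniform on 28 to 36): at t = 29.4, 0.605 × 6.6/8 = 0.499, so the plain median is 29.4.
- Onset in weeks 12 to 20 (F uniform on 16 to 24): at t = 19.1, 0.815 × 4.9/8 = 0.499, so the plain median is 19.1.

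The difference, 29.4 − 19.1 = 10.3 weeks, arises with no difference in durability.

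**The case against.** The strongest reply is that the SAP is silent rather than wrong. A reader might infer that it instructs the analyst to treat improvements present at week 36 as finished. It never says so, and a programmer could censor without contradicting any sentence in it. That stands as a limit on wording. But the bullet defines a number of weeks, the default for such a variable is descriptive, and the neighbouring bullet shows that censoring was written in where it was meant. Followed as written, the text gives truncated values.

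Second, week 36 is not the end of observation. The end-of-study visit reaches about week 40. The OLE collects blood counts, transfusion diaries and MPN-SAF every cycle, has duration beyond 36 weeks as a secondary objective (protocol Appendix J), and is covered by the final report. This is correct and reduces truncation for subjects who roll over. It does not remove it: improvements ongoing at the last OLE assessment meet the same gap, and everyone in the OLE receives 10 mg/kg, so OLE time no longer describes the randomized dose.

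Third, the size depends on assumptions chosen outside the documents, and the bias is not universal. This stands: with a true median of 16 weeks the plain median is unaffected and the mean falls by under a week.

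Fourth, the arms are randomized with the same visit schedule, so a reader should not infer that one dose will be favoured. This also stands. Distortion between arms requires onset or dropout to differ between them, and the documents give no data on either.

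Finally, the Stage 2 primary analysis had its own SAP (version 2.0, March 2018), which is cited but not available here. It may contain a rule. The SAP for the final analysis does not.

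**Conclusion.** The point holds in a limited form. SAP 4.4.2 leaves three secondary durations without an end event or censoring, and with default summaries the result is biased short when true durations are long relative to follow-up. Under the stated assumptions and a week-36 cut, the shortfall in the median is 0, 3.9, 13.5 and 39.8 weeks for true medians of 16, 24, 36 and 64 weeks. The true size cannot be determined from the documents. Arms can differ artificially if onset timing differs; that they will is not shown. No primary result is affected. Because the direction is predictable and the SAP already contains a suitable method, the change should be made.

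**What to change.** Amend the second Stage 2 duration bullet in SAP 4.4.2 to state:

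- **Start.** The first week of the first qualifying 12-week period. The present wording could mean the beginning or the end of that period.
- **Event.** The first assessment at which that endpoint's improvement criterion is no longer met, written out separately for hemoglobin, platelets and symptoms. The marrow event (return to baseline grade) does not transfer, and the rolling 12-week transfusion criteria need their own definition of loss.
- **Censoring.** The last evaluable main-stage assessment if the subject is still improved, including subjects who leave while improved.
- **Analysis.** Kaplan-Meier by dose, as for marrow response. A median that is not reached should be reported as such.
- **OLE.** Any duration extended with OLE data shown separately by original dose, because all OLE subjects receive 10 mg/kg.

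The cost is three short event definitions and a little extra programming. No new data are needed. Kaplan-Meier assumes that censoring at dropout is uninformative, so the number censored for withdrawal should be shown by arm.
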